10.2.1 Assessment of severity

Assessment of severity is one of the responsibilities of the investigator in the evaluation of AEs and SAEs. Severity will be graded according to the NCI CTCAE v4.03. The determination of severity for all other events not listed in the CTCAE should be made by the investigator based upon medical judgment and the severity categories of Grade 1 to 5 as defined below.

Grade 1 (mild)	An event that is usually transient and may require only minimal treatment or therapeutic intervention. The event does not generally interfere with usual activities of daily living.
Grade 2 (moderate)	An event that is usually alleviated with additional specific therapeutic intervention. The event interferes with usual activities of daily living, causing discomfort but poses no significant or permanent risk of harm to the subject.

Grade 3 (severe)	An event that requires intensive therapeutic intervention. The event interrupts usual activities of daily living, or significantly affects the clinical status of the subject.
Grade 4 (life threatening)	An event, and/or its immediate sequelae, that is associated with an imminent risk of death or with physical or mental disabilities that affect or limit the ability of the subject to perform activities of daily living (eating, ambulation, toileting, etc).
Grade 5 (fatal)	Death (loss of life) as a result of an event.

It is important to distinguish between serious criteria and severity of an AE. A Grade 3 AE need not necessarily be considered an SAE. For example, a Grade 3 headache that persists for several hours may not meet the regulatory definition of an SAE and would be considered a nonserious event, whereas a Grade 2 seizure resulting in a hospital admission would be considered an SAE.

10.3 Recording of adverse events and serious adverse events

Adverse events will be recorded using a recognized medical term or diagnosis that accurately reflects the event. Adverse events will be assessed by the investigator for severity, relationship to the investigational product, possible etiologies, and whether the event meets criteria of an SAE and therefore requires immediate notification to AstraZeneca/MedImmune Patient Safety.

The following variables will be collected and recorded in RedCap for each AE:

- AE (verbatim)
- The date when the AE started and stopped
- Changes in NCI CTCAE grade and the maximum CTC grade attained
- Whether the AE is serious or not
- Investigator causality rating against durvalumab or tremelimumab (yes or no)
- Action taken with regard to durvalumab + tremelimumab/comparator/combination agent
- Outcome

In addition, the following variables will be collected and recorded in RedCap for SAEs as applicable:

- Date AE met criteria for serious AE
- Date Investigator became aware of serious AE
- AE is serious due to <<criteria>>
- Date of hospitalization
- Date of discharge
- Probable cause of death
- Date of death
- Autopsy performed

- Description of AE
- Causality assessment in relation to Study procedure(s)

Events, which are unequivocally due to disease progression, should not be reported as an AE during the study.

10.3.1 Study recording period and follow-up for adverse events and serious adverse events

Adverse events and serious adverse events will be recorded from time of first protocol intervention, throughout the treatment period and including the follow-up period (90 +/-7 days after the last dose of durvalumab + tremelimumab).

During the course of the study all AEs and SAEs should be proactively followed up for each subject. Every effort should be made to obtain a resolution for all events, even if the events continue after discontinuation/study completion.

If a subject discontinues from treatment for reasons other than disease progression, and therefore continues to have tumor assessments, drug or procedure-related SAEs must be captured until the patient is considered to have confirmed PD and will have no further tumor assessments.

The investigator is responsible for following all SAEs until resolution, until the subject returns to baseline status, or until the condition has stabilized with the expectation that it will remain chronic, even if this extends beyond study participation.

Follow-up of unresolved adverse events

Any AEs that are unresolved at the subject's last visit (90 days post End of Treatment) in the study are followed up by the investigator for as long as medically indicated, but without further recording. After 90 days, only subjects with ongoing investigational product-related SAEs will continue to be followed for safety.

AstraZeneca/MedImmune and the IND Office retain the right to request additional information for any subject with ongoing AE(s)/SAE(s) at the end of the study, if judged necessary.

Post study events

After the subject has been permanently withdrawn from the study, there is no obligation for the investigator to actively report information on new AE or SAEs occurring in former study subjects after the 90-day safety follow-up period for patients treated with durvalumab + tremelimumab. However, if an investigator learns of any SAEs, including death, at any time after the subject has been permanently withdrawn from study, and he/she considers there is a reasonable possibility that the event is related to study treatment, the investigator should notify the study The University of Texas MD Anderson Cancer Center and AstraZeneca/MedImmune Drug Safety.

10.3.2 Investigator Communications with AstraZeneca

All SAE reports and accompanying cover pages will be sent, by way of email, to AstraZeneca's designated mailbox: [contact].

* A **cover page** should accompany the **MD Anderson IRB SAE** form indicating the following:

- “Notification from an Investigator Initiated Study”
- The MD Anderson IND number assigned by the FDA
- The investigator's name and address
- The trial name/title and AstraZeneca ISS reference number (ESR-##-#####)

* The University of Texas MD Anderson Cancer Center must also indicate, either in the SAE report or the cover page, the **causality** of events **in relation to all study medications** and if the SAE is **related to disease progression**, as determined by the principal investigator.

* **Send SAE report and accompanying cover page by way of email to AstraZeneca's designated mailbox:** [contact]

If a non-serious AE becomes serious, this and other relevant follow-up information must also be provided to AstraZeneca.

Serious adverse events that do not require expedited reporting to the FDA still need to be reported to AstraZeneca preferably using the MedDRA coding language for serious adverse events. This information should be reported on a monthly basis and under no circumstance less frequently than quarterly.

10.3.2.1 Reporting of deaths

All deaths that occur during the study, or within the protocol-defined 90-day post-last dose of durvalumab + tremelimumab safety follow-up period must be reported as follows:

- Death that is clearly the result of disease progression should be documented but should not be reported as an SAE.
- Where death is not due (or not clearly due) to progression of the disease under study, the AE causing the death must be reported to as a SAE within **24 hours** (see Section 10.3.2 for further details). The report should contain a comment regarding the co-involvement of progression of disease, if appropriate, and should assign main and contributory causes of death.
- Deaths with an unknown cause should always be reported as a SAE.

Deaths that occur following the protocol-defined 90-day post-last-dose of MEDI4736 and/or Tremelimumab safety follow-up period will be documented, but will not be reported as an SAE. If the death is possibly related to durvalumab and/or tremelimumab, it will be reported as an SAE.

10.3.3 Other events requiring reporting

10.3.3.1 Overdose

An overdose is defined as a subject receiving a dose of durvalumab + tremelimumab in excess of that specified in the Investigator's Brochure, unless otherwise specified in this protocol.

Any overdose of a study subject with durvalumab + tremelimumab, with or without associated AEs/SAEs, is required to be reported within 24 hours of knowledge of the event to The University of Texas MD Anderson Cancer Center and AstraZeneca/MedImmune Patient Safety or designee using the designated Safety e-mailbox (see Section 10.3.2 for contact information). If the overdose results in an AE, the AE must also be recorded as an AE (see Section 10.3). Overdose does not automatically make an AE serious, but if the consequences of the overdose are serious, for example death or hospitalization, the event is serious and must be recorded and reported as an SAE (see Section 10.3 and Section 10.3.2). There is currently no specific treatment in the event of an overdose of durvalumab or tremelimumab.

The investigator will use clinical judgment to treat any overdose.

10.3.3.2 Hepatic function abnormality

Hepatic function abnormality (as defined in Section 10.1.3.) in a study subject, with or without associated clinical manifestations, is required to be reported as "hepatic function abnormal" ***within 24 hours of knowledge of the event*** to The University of Texas MD Anderson Cancer Center and AstraZeneca/MedImmune Patient Safety using the designated Safety e-mailbox (see Section 10.3.2 for contact information), unless a definitive underlying diagnosis for the abnormality (e.g., cholelithiasis or bile duct obstruction) that is unrelated to investigational product has been confirmed.

- If the definitive underlying diagnosis for the abnormality has been established and is unrelated to investigational product, the decision to continue dosing of the study subject will be based on the clinical judgment of the investigator.
- If no definitive underlying diagnosis for the abnormality is established, dosing of the study subject must be interrupted immediately. Follow-up investigations and inquiries must be initiated by the investigational site without delay.

Each reported event of hepatic function abnormality will be followed by the investigator and evaluated by the The University of Texas MD Anderson Cancer Center and AstraZeneca/MedImmune.

10.3.3.3 Pregnancy

10.3.3.4 Maternal exposure

If a patient becomes pregnant during the course of the study, the IPs should be discontinued immediately.

Pregnancy itself is not regarded as an AE unless there is a suspicion that the IP under study may have interfered with the effectiveness of a contraceptive medication. Congenital abnormalities or birth defects and spontaneous miscarriages should be reported and handled as SAEs. Elective abortions without complications should not be handled as AEs. The outcome of all pregnancies (spontaneous miscarriage, elective termination, ectopic pregnancy, normal birth, or congenital abnormality) should be followed up and documented even if the patient was discontinued from the study.

If any pregnancy occurs in the course of the study, then the Investigator or other site personnel should inform the appropriate AstraZeneca representatives within 1 day, ie, immediately, but **no later than 24 hours** of when he or she becomes aware of it.

The designated AstraZeneca representative will work with the Investigator to ensure that all relevant information is provided to the AstraZeneca Patient Safety data entry site within 1 to 5 calendar days for SAEs and within 30 days for all other pregnancies.

The same timelines apply when outcome information is available.

10.3.4 Paternal exposure

Male patients should refrain from fathering a child or donating sperm during the study and for 180 days after the last dose of durvalumab + tremelimumab combination therapy, whichever is the longer time period.

Pregnancy of the patient's partner is not considered to be an AE. However, the outcome of all pregnancies (spontaneous miscarriage, elective termination, ectopic pregnancy, normal birth, or congenital abnormality) occurring from the date of the first dose until 90 days after the last dose should, if possible, be followed up and documented.

Where a report of pregnancy is received, prior to obtaining information about the pregnancy, the Investigator must obtain the consent of the patient's partner. Therefore, the local study team should adopt the generic ICF template in line with local procedures and submit it to the relevant Ethics Committees (ECs)/Institutional Review Boards (IRBs) prior to use.

11. STATISTICAL METHODS AND SAMPLE SIZE DETERMINATION

11.1 Description of analysis sets

11.1.1 Safety analysis set

All patients who receive at least one dose of study drug will be included in the safety monitoring and safety analysis.

11.1.2 Efficacy analysis set

All enrolled patients will be included in the primary feasibility analysis. Only patients with surgical specimens and immune measures will be included in secondary and exploratory analyses requiring that information.

11.2 Goals

Since this combination has not been previously evaluated in the presurgical setting in hormone receptor positive, HER2 negative breast cancer, this trial will: 1) assess the feasibility of enrolling patients onto a trial evaluating investigational agents prior to initiating standard neoadjuvant chemotherapy, 2) determine the safety of durvalumab and tremelimumab in patients with hormone receptor positive, HER2 negative breast cancer, as well as 3) gather preliminary immunologic information for designing future trials.

11.3 Endpoints

11.3.1 Primary Endpoints

The primary endpoints will be

:

1. Feasibility. This will be measured by 2 achievements. If both are met, then upfront treatment with durvalumab plus tremelimumab will be feasible for future trials in these breast cancer patients. Otherwise, other strategies for implementing these treatments will need to be designed. The 2 measures are:
 - a. Patients are willing to enroll: This will be established if we can enroll all 15 patients within 12 months of starting the study. The start date for measuring feasibility will be the date the first patient is screened.
 - b. Patients can complete the protocol: If at least 10 patients complete the study and have available immune data the trial meets this feasibility criterion. If fewer than 8 finish then this dose/schedule is infeasible. If 8 or 9 complete the study with immune data then clinical judgment combining toxicity, efficacy, and physician

experience with the protocol will be used to determine whether adjustments to the treatment are needed before a future trial.

2. Adverse events will be recorded according to CTCAE 4.03.

11.3.2 Secondary Endpoint

Immune and molecular measures in peripheral blood and tumor tissues pre and post treatment.

11.3.3 Exploratory Endpoint

Pathologic response at surgery will be recorded for each patient.

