This trial platform is similar to that employed by our collaborator [name]. A previous study performed at MD Anderson by [name] evaluated the use of an anti-CTLA-4 antibody (ipilimumab) as pre-surgical therapy in patients with localized urothelial carcinoma of the bladder (Carthon et al 2010). Immunological analyses of pre- and post-treatment tumor tissues indicate that ipilimumab therapy resulted in significant activation of immune cells and infiltration of immune cells into tumor tissues (Chen et al 2009; Liakou et al 2008). The rationale for combining durvalumab and tremelimumab is that the mechanisms of CTLA-4 and PD-1 are non-redundant, suggesting that targeting both pathways may have additive or synergistic activity (Pardoll 2012). This has been demonstrated in preclinical models (Curran et al 2011; Duraiswamy et al 2013) as well as in clinical trials where combining immunotherapy agents has been shown to result in improved response rates (RRs) relative to monotherapy. For example, the concurrent administration of nivolumab and ipilimumab to patients with advanced melanoma induced higher objective response rates (ORRs) than those obtained with single-agent therapy. Importantly, responses appeared to be deep and durable (Wolchok et al 2013). Similar results have been observed in an ongoing study of durvalumab + tremelimumab in NSCLC (Antonia et al 2014), with further updated details presented in this clinical study protocol.

This study will allow us to evaluate the feasibility of enrolling patients with HR+/HER2- breast cancer onto a trial evaluating investigational immunotherapeutic agents prior to initiating standard neoadjuvant chemotherapy, and to evaluate the safety and tolerability of the combination of tremelimumab plus durvalumab in patients with HR+/HER2- breast cancer. Importantly, we will also be able to assess the immunologic/molecular responses to the combination of tremelimumab plus durvalumab in patients with

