HR+/HER2- breast cancer as well as to evaluate the pathologic response in HR+/HER2- breast cancer patients receiving the combination prior to initiation of standard neoadjuvant chemotherapy. The study will therefore allow us to test the clinical activities of these immune checkpoint therapies against HR+/HER2- breast cancer as well to identify biomarkers to guide potential use of these agents in the setting of HR+/HER2- breast cancer. The study will therefore inform the design of subsequent studies evaluating these agents in both the neoadjuvant setting for patients with disease as well as in the setting of metastatic HR+/HER2- breast cancer.

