2.1.3 Exploratory objective

To evaluate the pathologic response in patients with HR+/HER2- breast cancer receiving tremelimumab plus durvalumab prior to initiating standard neoadjuvant chemotherapy.

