3. STUDY DESIGN

3.1 Overview of study design

This is an open-label, single-arm, presurgical pilot study in patients with HR+/HER2- breast cancer.

[figure not shown]
There will be 15 patients enrolled.

Patients will receive durvalumab at 1500 mg plus tremelimumab at 75 mg every 4 weeks for a total of 2 doses. A standard regimen of neoadjuvant chemotherapy will be initiated within 4 weeks after the last infusion of durvalumab and tremelimumab. A biopsy will be obtained after the last infusion of durvalumab and tremelimumab before neoadjuvant chemotherapy is started.

Patients will undergo surgery after the completion of standard neoadjuvant chemotherapy.

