6. TREATMENT PLAN

6.1 Subject enrollment

Patients who have signed informed consent and have undergone screening will be enrolled onto this study and can begin therapy. There is no randomization. This is a single arm, open-label presurgical pilot study prior to the initiation of standard neoadjuvant chemotherapy of the physician's choice for patients with clinical stage II-III HR+/HER2- breast cancer. Patients who are unable to complete all

scheduled study requirements including the pre and post treatment breast biopsies can be replaced at the request of [name] and/or [name] and/or the study team.

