8.1.3 End of Treatment

End of treatment is defined as the last planned dose of tremelimumab and durvalumab. This will be followed by physician's choice of systemic therapy, followed by standard of care surgical intervention. Any further adjuvant therapy is at the discretion of the treating physician. Also, should the treating physician deem it is in the patient's best interest to proceed with surgery after the completion of the 2 doses each of tremelimumab and durvalumab, the physician may proceed with surgery with adjuvant therapies as per physician discretion.

All subjects will be followed until the time of breast surgery.

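### Does measuring pathologic response after chemotherapy mean that the pre-chemotherapy ultrasound volume has to be added to the Section 11 endpoints?

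*Combined protocol and SAP*

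**What the plan says.** Section 1.3 names two kinds of response. On the immune side, "we will also be able to assess the immunologic/molecular responses to the combination of tremelimumab plus durvalumab in patients with" this disease; on the tumor side, the study is "to evaluate the pathologic response in HR+/HER2- breast cancer patients receiving the combination prior to initiation of standard neoadjuvant chemotherapy". It then concludes: "The study will therefore allow us to test the clinical activities of these immune checkpoint therapies against HR+/HER2- breast cancer".

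The exploratory objective in 2.1.3 is "To evaluate the pathologic response in patients with HR+/HER2- breast cancer receiving tremelimumab plus durvalumab prior to initiating standard neoadjuvant chemotherapy". The matching endpoint in 11.3.3 is "Pathologic response at surgery will be recorded for each patient". Section 9 makes this concrete as Residual Cancer Burden (RCB), recorded as a continuous score and in four classes.

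On timing, Section 3.1 states: "Patients will undergo surgery after the completion of standard neoadjuvant chemotherapy". Section 6.1 adds: "There is no randomization. This is a single arm, open-label presurgical pilot study prior to the initiation of standard neoadjuvant chemotherapy", with the regimen left to the physician. Section 8.1.3 allows an exception: after the two doses of each drug, "the physician may proceed with surgery with adjuvant therapies as per physician discretion".

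Ultrasound is covered outside Section 11. Footnote 11 of the Schedule of Study Assessments defines tumor volume as length × width × height × π/6, to be used for estimating change in the breast tumor between baseline and the end of investigational therapy. The schedule places the repeat scan in the column before neoadjuvant therapy. Section 9 makes mammogram and ultrasound the main baseline evaluations and repeats the ultrasound after the two cycles. Sections 11.1 to 11.6 mention neither ultrasound nor tumor volume.

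**The concern.** A patient who follows the default path has received two doses of each antibody and then a full course of chemotherapy before pathologic response is read. With no control arm and no benchmark, a low RCB could come from the chemotherapy, the antibodies or both. If a few patients go straight to surgery under 8.1.3, the same endpoint mixes response to the antibodies alone with response to the whole sequence. Set against the activity statement in 1.3, this looks like an endpoint that cannot answer the question asked of it.

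Meanwhile a measure taken before chemotherapy is collected but absent from the endpoint list. At stake would be a report that leans on post-chemotherapy pathology as evidence of drug activity and carries that reading into the later neoadjuvant and metastatic trials that 1.3 mentions.

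**Working it through.** No sample size, power or error rate is in dispute, so the check consists of setting the sections side by side.

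1. **Can pathologic response be attributed to the combination?** Sections 3.1, 3.2 and 6.1 give the sequence: two doses four weeks apart, chemotherapy within 28 days of the last infusion, and surgery within 8 weeks of completing it, all in one unrandomized arm. It cannot, except descriptively in any patient who goes directly to surgery under 8.1.3. This part of the concern is right.

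2. **Does an operative section make that attribution?**
   - Section 2.1.3 describes response in patients who received the combination; it does not claim response caused by it.
   - Section 11.2 lists the goals as feasibility, safety and preliminary immunologic information. Tumor activity is not among them.
   - Section 11.3.3 commits only to recording pathologic response.
   - Section 11.4 says no hypothesis is formally tested.
   - Section 11.6 sets no pathologic response rate, comparison or threshold.
   - The numerical decision rules are 15 patients enrolled within 12 months, at least 10 completers with immune data (fewer than 8 being infeasible), the extreme-toxicity stopping boundaries, and 6 or more extreme toxicities. None of them uses pathologic response.

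   The mismatch is therefore confined to one sentence of rationale. That sentence also follows the mention of immune responses, which rest on paired biopsies taken before chemotherapy (8.3.1) and are not confounded in this way.

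3. **Is the better-attributed measure lost?** No. Footnote 11 supplies the formula, interval and purpose; the schedule and Section 9 supply both scans. Nothing further has to be collected.

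4. **Does the plan say how to summarize it?** Section 11.6 promises descriptive statistics, with differences or percent changes, for blood and tumor measures. That could include ultrasound volume. The narrower reading is the more natural one: the next sentence of 11.6 speaks of samples, 11.3.2 of blood and tumor tissues, and 11.4 pairs tumor with blood for immune and molecular changes. On that reading there is a gap. An analyst holding two volumes per patient and the stated purpose in footnote 11 would fill it with the same within-patient percent change, which also remains defined (−100%) if a tumor is no longer measurable.

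5. **What would listing it alter?** The same scans, the same patients and an uncontrolled descriptive summary would result. A precision calculation for the mean change would need a standard deviation that the documents do not give, and it would not show any conclusion moving.

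**The case for a change.** The strongest case for a change is that it costs a few lines and no new data. Section 1.3 presents clinical activity as separate from biomarker discovery, so it cannot simply be read as immune activity. Section 9 treats ultrasound as a main disease evaluation, yet Section 11 is silent on it. Section 11.6 gives no explicit summary for RCB, and 8.1.3 allows two different surgical settings without a rule for separating them. In addition, 11.3.1 lets efficacy enter the judgment if 8 or 9 patients complete, without saying which measure is meant; 11.1.2, headed as the efficacy analysis set, defines populations only.

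As a description of the text, all of this stands. It falls short of a reason to amend. An exploratory score recorded for at most 15 patients will be listed and tabulated without special instruction. Because 8.1.3 has every patient followed to breast surgery, it should be known who had chemotherapy first, and the two groups can be shown apart. The 8-or-9 clause is expressly left to clinical judgment and weighs toxicity and physician experience as well. Naming a measure there would not turn it into a rule, and the point is separate from confounding by chemotherapy.

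The ultrasound change is not a clean answer either. It has no control, and inflammatory swelling or the baseline core biopsies may affect it. A summary restricted to patients scanned after both cycles would also leave out those who stopped after one dose.

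**Conclusion.** The text supports the observation: the only tumor-response endpoint listed in 11.3 is, by default, read after chemotherapy, and Section 11 omits the ultrasound volume. No change to the plan follows. The measure is already defined and scheduled elsewhere in the same document, the exploratory endpoint agrees with its own objective, and no test or numerical decision rule depends on either. The effect on the primary feasibility and safety results is nil. What remains is a risk of misreading, limited to exploratory results in a pilot of 15.

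This rests on two assumptions: that the analysts use footnote 11 for the purpose it states, and that the report describes RCB after chemotherapy as the result of the whole treatment sequence. Both are ordinary practice.
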